cRCT sample. The villages in which we are conducting this study are subsistence farming communities with high levels of poverty and malnutrition in three regions of Senegal: Thies, Diourbel and Fatick. Each of the 104 villages that will be included in the study have been purposively selected to ensure that they have an established farming group, and that they are sufficiently geographically dispersed in order to minimize risk of contamination. We will use the list of the household members of the farming groups of each of the 104 villages included in the cRCT as our sampling frame. Based on [name] previous experience, we will identify all households within the farming group that have a child 6-19 months of age at baseline (to ensure that the child is not >23 months at endline), and we will subsequently randomly select five mother, father and child triads to be included in our study sample. In some cases, the primary caregiver of the child may be a close relative rather than the birth mother. In these instances, the primary caregiver will receive the voice and text messages along with her husband or primary male caregiver. In total, we will sample 510 triads in 104 villages (~5 households/triads per village). Thus, our sample will include 510 mother, father and child triads. Baseline data collection will take place in May/Jun 2022, the intervention will be delivered between Jun-Sep 2022 and the endline data collection will take place in October 2022.

Process Evaluation sample: A smaller purposive sample of approximately 45 mothers and fathers, implementation project staff and CHWs will be included in Aim 2 of the project as part of the in-depth semi-structured interviews and focus groups conducted in the process evaluation. We will purposively select three villages from each region (n total = 9 villages) in order to maximize variation in village characteristics such as size, distance to urban settings, distance to markets, etc. Interviewees and focus group participants will be purposively selected from the list of all mothers and fathers receiving the voice messages in each of these villages to ensure variation in participant socio-demographics (e.g., household size, parity, age, etc.) as well as key people involved in the intervention's implementation. The process evaluation data collection will take place in between October and December 2022.

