Household survey: Consenting participants (mothers and fathers) will complete a household survey that will include information regarding demographics, household characteristics, household expenditures (including healthcare and food expenditures), food insecurity, and infant and young child feeding (IYCF) knowledge, attitudes, beliefs, norms, intentions and behavior. Either the mother or father will answer the questions related to demographics and household characteristics. Both mothers and fathers will separately answer IYCF knowledge, attitudes, beliefs, norms, intentions survey questions. Given that mothers are the primary caregiver of their young children, we will ask mothers to report on the frequency of consuming specific foods targeted in the intervention using a food frequency questionnaire (FFQ) as well as the list-based 24-hour dietary recall, described below. This is typical of collecting dietary data for infants and young children, given that the mother is generally the primary person feeding their children. This is particularly true in the Senegalese culture, where women are the primary caregivers of their

children. The enumerator will record all verbal answers to the household survey questions in an electronic tablet.

List-based 24-hour dietary recall: A list-based 24-hour dietary recall will be conducted with women to assess the dietary intakes of their children. This involves assessing whether their child consumed a list of foods and beverages (including breast milk) over the past 24 hours. Based on the dietary recall we will calculate the minimum acceptable diet (MAD) which measures the proportion of children aged 6-23 months who: had meal frequency the previous day that met the minimum standard for their age as defined by the WHO; AND consumed foods from at least 4 of the 7 food groups identified by the indicator.

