In addition to the 8 scripted messages, we will send an additional 8 unscripted role modeling messages, that describe strategies used by "positive deviants" to successfully adopt the key targeted behaviors. The intervention will be delivered over a 16-week period, which falls within the duration observed in previously published IYCF messaging interventions that demonstrated positive impacts.¹⁰ One voice and one text message will be sent each week over the 16-week period, which is aligned with both the previously published literature¹⁰ as well as the community preferences identified through our formative work.

We will not provide participants with phones as part of this intervention. Cell phone ownership is very high in these communities. In most cases, adults have their own phones. In the event that the man or woman participating in the study do not have their own phone, we will ask them if there is a phone that they have access to in the household. In this situation, we will send the voice messages to that phone. However, if they do not have access to a phone we will not continue the recruitment process. There will be no costs to the participants receiving the messages. We will cover all costs of sending the messages and the minutes spent sending them. Using a combination of voice and text messages will enable us to ensure that messages reach phones in areas with poor mobile coverage, while also accounting for literacy levels. Baseline and endline surveys will be conducted in both the control and experimental groups. The control group will receive the 16 messages after the completion of data collection.

Randomization of intervention: Computer-generated random numbers will be used to randomize 104 villages in a 1:1 allocation, stratified by village size (number of households per village) and region (Thiès, Diourbel, Fatick), to receive either the intervention (experimental group) or usual care (control group). Randomization will be conducted following a baseline survey and, given the nature of the intervention, will not be blinded. The intervention will be delivered over a 16-week period.

Data collection for process and economic evaluation:

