1.5 Sample Size Justification

We expect to enroll 510 mother, father and child triads in 104 villages (clusters) in the Thies, Diourbel and Fatick regions of Senegal as part of this study. We plan to include ~5 triads per village. Our sample size estimation was calculated based on our two primary outcomes: the prevalence of MAD and anemia.

The sample size estimate is informed by our prior cross-sectional research on over 1200 household surveys and our pilot data over a 4-week intervention period (unpublished data).² Attrition was 2%, anemia prevalence was 66% and MAD prevalence was 46.8%. Assuming a conservative intra-class correlation coefficient of 0.02,³ 5% attrition (based on our pilot work and previously published community-based research projects in Senegal),^{29,30} and a 2-sided significance level of 0.05, 102 clusters with 5 triads per cluster will provide 81.7% power to detect a 6% absolute difference in anemia and 88.8% power to detect an absolute difference of

7% in MAD. Our pilot study found a 19.2% increase in MAD. Even if we assume 10% attrition, we will still have 80% power to detect a 6% absolute difference in anemia and 87.3% power to detect an absolute difference of 7% in MAD. Improvements in anemia and MAD prevalence of 6% and 7%, respectively are clinically relevant and aligned with improvements in previously published studies.^{31,32}

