6.0 Data Management Plan

6.1 Data Analysis

Cognitive testing: As mentioned previously, we will take detailed notes during the cognitive testing. The notes will be subsequently analyzed by members of the study team ([name] & [name]) by assessing common themes/patterns in the message comprehension. Summaries that describe the issues noted for each message and how they were addressed will then be prepared and discussed as a team, in an iterative way until the point of theoretical saturation.

cRCT: To estimate the impact of the mHealth messaging intervention on anemia and MAD, as well as our secondary outcomes, we will utilize a difference-in-differences approach. Linear regression models will be fitted for each outcome, with explanatory variables that include the intervention indicator, time (baseline and endline), and intervention by time interaction. The interaction term is of primary interest, as it summarizes mean changes in the outcome before and after the intervention in the treatment group compared with the control group. The intervention variable is as randomized (intention to treat). We anticipate that the parallel trend assumption will hold in this scenario since the various clusters and triads within clusters are similar to each other socio-economically; however, we will carefully test this assumption by applying the recently developed difference-in-difference model checklist⁴. We will analyze the data on the individual level and use generalized estimating equation (GEE) extensions of regression in SAS 9.4 to account for clustering. All models will adjust for sex of the child, socioeconomic status of the family and highest education completed by the mother. We will also conduct exploratory subgroup analyses based on baseline anemia status.

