Study Title: The Impact and Implementation of a Mobile Messaging Intervention to Improve Infant and Young Child Nutrition in Senegal

NCT Number: NCT05374837

Document date: 05/21/24

Document name: Statistical Analysis Plan

STATISTICAL ANALYSIS PLAN

Study outcomes: Table 1 provides an overview of our study outcomes.

Table 1. Overview of study outcomes

Outcome type	Outcome	Description
Primary	Anemia prevalence	We will use Hemocue Hb301 machines to measure hemoglobin levels in children in order to determine anemia prevalence using the WHO cut-offs: mild $10 \leq \text{hb} < 11 \text{ g/dl}$; moderate $7 \leq \text{hb} < 10 \text{ g/dl}$ and severe $\text{hb} < 7 \text{ g/dl}$. A finger prick will be used to obtain a drop of capillary blood that is placed on a cuvette and inserted in the Hemocue machine to obtain an on-the-spot assessment of hemoglobin levels.
	Minimum Acceptable Diet	Minimum Acceptable Diet Prevalence, Primary, baseline and endline: The minimum acceptable diet indicator will be used to assess dietary diversity in children. A 24-hour open dietary recall will be conducted with mothers to assess their child's dietary intake over the previous day. The 24-hour recall will be used to calculate minimum dietary diversity (MDD) (consuming ≥ 4 of 7 food groups (grains, roots and tubers; legumes and nuts; dairy products; flesh foods; eggs; vitamin A rich fruits and vegetables; other fruit and vegetables)) and minimum meal frequency (MMF) (2x/day for breastfed infants 6-8.9 months; 3x/day for breastfed children 9-23.9 months; 4x/day for non-breastfed children 6-23.9 months). Children who meet the thresholds for both MDD and MFF are defined as consuming a MAD, based on the WHO/UNICEF IYCF indicator.
Secondary	Frequency of consuming key foods in past 7 days	Frequency of consuming key foods in the past 7 days, Secondary, baseline and endline: We will use a 7-day food frequency questionnaire (FFQ) to assess the frequency that children consumed specific foods targeted in the intervention over the course of the previous week. More specifically, the FFQ will ascertain the number of times that the following foods have been consumed: eggs, leafy greens, fish, milk, cowpea, nuts, orange colored fruits and vegetables, other fruits and vegetables, thick porridge, beef or mutton, pork, chicken and liver.

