Description of Statistical Approach: To estimate the impact of the mHealth messaging intervention on anemia and MAD, as well as our secondary outcomes, we will utilize a difference-in-differences approach. Linear regression models will be fitted for each outcome, with explanatory variables that include the intervention indicator, time (baseline and endline), and intervention by time interaction. The interaction term is of primary interest, as it summarizes mean changes in the outcome before and after the intervention in the treatment group compared with the control group. The intervention variable is as randomized (intention to treat). We anticipate that the parallel trend assumption will hold in this scenario since the various clusters and triads within clusters are similar to each other socio-economically; however, we will carefully test this assumption by applying the recently developed difference-in-difference model checklist⁴. We will analyze the data on the individual level and use generalized estimating equation (GEE) extensions of regression in SAS 9.4 to account for clustering. All models will adjust for sex of the child, and highest education completed by the mother. We will also conduct exploratory subgroup analyses based on baseline anemia status.

References

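### The difference-in-differences models list no randomisation strata, so the standard error can be slightly too wide; separately, protocol and SAP name different covariates for all models.

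*Protocol*

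**What the plan says.** **Allocation.** Protocol 1.3 (Randomization of intervention) randomises 104 villages 1:1, "stratified by village size (number of households per village) and region (Thiès, Diourbel, Fatick"). The number of size categories and their cut-points are not given.

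**Model.** Protocol 6.1 and the SAP (Description of Statistical Approach) specify linear models with arm, time and arm-by-time, fitted by GEE on individual data. Neither lists region, village size or a stratum-by-time term.

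**Covariates.** Protocol 6.1: "All models will adjust for sex of the child, socioeconomic status of the family and highest education completed by the mother". SAP: "All models will adjust for sex of the child, and highest education completed by the mother". The two analysis paragraphs are otherwise nearly identical.

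**Context.** Both documents expect parallel trends because "the various clusters and triads within clusters are similar to each other socio-economically", and both plan to check that assumption. The household survey covers "household expenditures (including healthcare and food expenditures), food insecurity" among other items and is run at baseline and endline. The SAP header reads "Document date: 05/21/24"; protocol 1.3 states that "the endline data collection will take place in October 2022".

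**The concern.** Stratified allocation balances the arms on region and size. If strata change differently between surveys, that difference adds almost nothing to the true sampling error of the arm-by-time estimate. A model without stratum-by-time terms still counts it as unexplained between-village variation, so the reported standard error exceeds the true one and the test becomes conservative.

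The covariate conflict is a different problem. Two current documents each define all models, and they disagree on whether socioeconomic status is included. Until one governs, both primary outcomes have two candidate analyses, and the more favourable could be reported. Socioeconomic status is not defined, and nothing says whether its baseline or a re-measured value would be used, so the protocol's own set is not a single model either.

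**Working it through.** **The plan's own figures.** The documents give no standard error for this point. Protocol 1.5 states power of 81.7% (anemia, 6 points) and 88.8% (MAD, 7 points). A two-proportion calculation from its inputs uses 255 × 0.95 = 242.25 per arm. The design effect is 1 + (4.75 − 1) × 0.02 = 1.075, so the effective n is 225.3.
- Anemia, 66% against 60%: SE = √[(0.66×0.34 + 0.60×0.40)/225.3] = 0.0454; z = 0.06/0.0454 = 1.32; power = Φ(1.32 − 1.96) = 26%.
- MAD, 46.8% against 53.8%: SE = 0.0470; z = 1.49; power = 32%.

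The stated power is not reproduced. That is a separate matter on which this point does not rest, but it explains the low base power below.

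**Approximate size of the excess.** With 52 villages per arm, the true variance of the estimate is about (4/104)·σ²w, where σ²w is the within-stratum variance of village change. The planned model reports about (4/104)·(σ²w + σ²b), where σ²b is the between-stratum variance of change. The ratio of standard errors is √(1 + σ²b/σ²w). For two equal size strata that differ by g in their change, σ²b = (g/2)².
- Simulated true SDs of 0.0531 (anemia) and 0.0556 (MAD) give σ²w = 26 × SD² = 0.0733 and 0.0804.
- g = 8.9 to 9.7 points: σ²b = 0.0020 to 0.0024; ratio 1.01 to 1.02.
- g = 17.7 to 19.2 points: σ²b = 0.0078 to 0.0092; ratio 1.05 to 1.06.

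**Simulation.** 6,000 trials per scenario.
- From the documents: 104 villages × 5 triads, 5% attrition, prevalence 66% and 46.8%.
- Assumed: 3 regions × 2, 3 or 4 size categories; arms balanced within cells; latent variances 0.03 (village), 0.27 (child) and 0.70 (residual); stratum main-effect SD 0.22; independence working correlation, identity link.
- Monte Carlo error is about ±0.6 points on type I error and ±1.1 on power, so smaller power differences should be read as no detectable change.

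Planned model, uncorrected standard error:

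| Gap between strata in their change | Reported SE / true SD | Type I error |
|---|---|---|
| None | 0.97–1.00 | 4.9–6.0% |
| 8.9–9.7 points | 0.99–1.01 | 5.1–5.5% |
| 17.7–19.2 points | 1.01–1.06 | 4.1–5.1% |

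Stratum-by-time terms that match the trends, with a Kauermann-Carroll standard error and t reference, give ratios of 0.97 to 1.02 and type I error of 4.4 to 5.5% in every scenario. With the uncorrected standard error, the same terms give type I error of 5.3 to 6.6% (two size categories) or 5.4 to 7.2% (three or four).

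Worked case, two size categories, larger trends by size (power with Kauermann-Carroll and t in both models):

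| | True SD | Planned SE | SE with terms, uncorrected | SE with terms, corrected | Power |
|---|---|---|---|---|---|
| Anemia, 6 points | 0.0531 | 0.0550 (ratio 1.04) | 0.0514 (0.97) | 0.0527 (0.99) | 17.9% → 21.2% |
| MAD, 7 points | 0.0556 | 0.0578 (1.04) | 0.0538 (0.97) | 0.0552 (0.99) | 21.3% → 24.5% |

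Across scenarios the power change is −0.2 to +0.1 points with no trends, +1.0 at 9 to 10 points apart and +1.8 to +3.3 at 18 to 19 points apart, on a base of 16 to 22%. If trends vary by region-by-size cell, additive terms leave the corrected standard error 4 to 6% too wide; cell-by-time terms give a ratio of 1.00 to 1.02.

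**Second simulation, other assumptions** (3,000 runs; six strata; region changes of ±5, ±10 or ±15 points plus smaller size changes). Ratios are 1.02, 1.09 and 1.12 for anemia and 1.01, 1.04 and 1.09 for MAD; test size falls as low as 3.0%. Stratum main effects alone change nothing (anemia at ±10: SE 0.0552 either way). Under simple randomisation with the ±10 trends, the true SD is 0.0571 instead of 0.0506 and the reported SE is again 0.0552. The excess width therefore comes from ignoring the stratified allocation.

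**Covariate sets.** If socioeconomic status is fixed at baseline and every child has both surveys, adding it leaves the arm-by-time estimate exactly unchanged. Otherwise, assuming an effect of 0.2 or 0.4 latent SD per SD, and a between-survey correlation of 0.7 when re-measured:

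| | Mean shift (points) | As share of SE (5.1–5.6 points) | Rise in type I error if either set may be reported |
|---|---|---|---|
| Fixed, 5% attrition | 0.12–0.24 | 0.12/5.6 = 2% to 0.24/5.1 = 5% | 0.1–0.3 points |
| Re-measured | 0.41–0.83 | 0.41/5.6 = 7% to 0.83/5.1 = 16% | 0.4–1.1 points |

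The largest rises are 5.13% to 5.40% (fixed) and 5.58% to 6.63% (re-measured).

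**The case against.** The strata omission does little harm. It biases nothing and does not inflate type I error. A visible penalty needs strata that diverge by about 18 points, some 2.5 to 3 times the 6- and 7-point effects the trial targets, and no passage gives a stratum trend. The model description is worded as an open list, so the strata are unstated rather than excluded. The added terms are safe only with a second change, the corrected standard error. The covariate effect is also small, its larger figures need socioeconomic status to be re-asked at endline, which no passage states, and the SAP is the natural governing document. The SAP date may be only a posting date.

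Most of this stands as a limit on size. The trends are assumptions, and the two simulations differ (1 to 6% against 1 to 12%) because their assumptions differ. The expectation of socio-economic similarity neither supports nor excludes different trends, and the planned parallel-trends check concerns arms, not strata. The protocol does intend to compare diet costs across communities and seasons, so differing change is at least open. The objection does not remove the textual conflict: nothing says that the SAP supersedes the protocol, or when and why socioeconomic status was dropped. The documents do not show whether outcomes had been seen by arm, and this point does not claim that they had.

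**Conclusion.** Both parts hold, and both are modest. Without stratum-by-time terms, the standard error is about right if strata share a trend and mildly too wide if they do not: 1 to 6% at an assumed gap of 18 to 19 points, and up to 12% under the second simulation's larger assumed trends. The fault is conservative. The remedy makes the reported standard error match the true sampling error; it does not reduce that error. The covariate conflict is certain from the text and leaves the primary model for anemia and MAD unfixed. Its numerical effect is near nil with baseline socioeconomic status and small with a re-measured value. Confidence in the sizes is medium, because stratum trends, size categories, variance components and socioeconomic effects are all assumed. The changes should be made because they cost little.

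**What to change.** 1. State in the SAP whether outcome data have been seen by arm.
2. If not, add the strata actually used for allocation as stratum-by-time terms with their main effects, and state the size categories. Use cell-by-time terms if villages were allocated within region-by-size cells. Pair them with a Kauermann-Carroll or Mancl-DeRouen sandwich standard error and a t reference based on the number of villages. Do not add the terms with the uncorrected standard error.
3. If outcomes have been seen by arm, keep the stated model as primary and report the stratum-by-time model as a labelled sensitivity analysis.
4. Name one covariate set for the primary model, say which document governs, and give the date and reason for removing socioeconomic status. If it is kept, define it and use its baseline value. Report the other set as a labelled sensitivity analysis.

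**Cost.** Before outcomes are seen, the cost is SAP wording and a corrected-variance option. Additive terms use (3 − 1) + (k − 1) degrees of freedom for k size categories: 3, 4 or 5 for k = 2, 3 or 4. Cell terms use 3k − 1: 5, 8 or 11, out of 104 villages. Simulated power loss when strata share a trend is at most 0.2 points, within Monte Carlo error. Afterwards, the strata part costs one extra sensitivity analysis. No new data are needed, since the planned household survey can supply socioeconomic status.

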1.4 Preliminary Data

We previously conducted a pilot of a modified version of this intervention. In our pilot research, we conducted focus groups (n=6) with mothers and fathers of young children, and completed a comprehensive survey of ~1200 households in Senegal, to identify key IYCF practices to target. We then developed 8 voice messages (based on the theory of planned behavior (TPB)²⁰) targeting the identified IYCF practices and conducted a pre- and post-intervention pilot study to examine its feasibility and potential for impact with a small sample of mother, father and child (6-23 months of age) triads (n=47).²¹ After the intervention, we found an improvement in the consumption of nutrient-rich foods and a greater proportion of children consuming a minimum acceptable diet (MAD) (19% higher in intervention as compared to the control group),²¹ an indicator of dietary diversity that is associated with nutrient adequacy, reduced stunting and underweight in children.²² However, we were limited by a small sample size and a lack of control group, which this study is designed to overcome.

